**Consultant:**

[name], CRNP, PhD

Johns Hopkins University

St. Jude Children's Research Hospital  
[name]  
[name]  
[contact]

Contents of this document may not be extracted without permission from the Principal Investigator.

**Protocol MNEMONIC and Title: SLEEPWELL: eHEALTH INSOMNIA  
INTERVENTION FOR ADULT SURVIVORS OF CHILDHOOD CANCER: A  
RANDOMIZEDCLINICAL TRIAL**

**Principal Investigators:** [name] & [name]

**IND Holder:** Not Applicable

**Brief Overview:** There is evidence that survivors of childhood cancer have a high prevalence of poor sleep, including symptoms of insomnia. Insomnia is highly comorbid and has been associated with impaired cognitive performance, a range of psychiatric disorders, cardiovascular disease, and reduced quality of life. However, we still lack knowledge about the direct impact of available internet-based insomnia treatment programs for survivors of childhood cancer experiencing insomnia, in addition to how improving insomnia symptoms impacts neurocognitive function and late health morbidities in this population. Therefore, in this study, we will utilize the resources available in the Childhood Cancer Survivor Study (CCSS) to use an accepted, established, efficacious internet-delivered CBTi insomnia treatment program and evaluate the efficacy of this program in adult survivors of childhood cancer. We are leveraging two electronic health platforms to treat insomnia and facilitate data collection. Positive results from this study and our use of an internet-based intervention are likely generalizable and be scalable to the large and geographically diverse population of childhood cancer survivors with chronic health conditions. The CCSS provides a unique opportunity for cost-effective evaluation of the efficacy of remote treatment of insomnia in such a large sample of childhood cancer survivors.

**Protocol MNEMONIC and Title: SLEEPWELL: eHEALTH INSOMNIA  
INTERVENTION FOR ADULT SURVIVORS OF CHILDHOOD CANCER: A  
RANDOMIZEDCLINICAL TRIAL**

**Evaluation:** Eligible participants will complete a 9-week internet-based insomnia treatment program or receive sleep education, depending on group assignment. CCSS participants who have been previously identified as having neurocognitive impairment will be approached for recruitment. An approach packet consisting of an introduction letter, a single page study brochure, and informed consent documents will be mailed to potentially eligible participants. Interested participants will be able to return the consent via mail using a pre-paid envelope. Alternatively, the packet will include instructions for visiting the study webpage, where participants can sign-up and provide informed consent on-line. Those who have not responded after two weeks will receive an email alerting them to the study and providing a link to the study webpage. Starting three weeks after the initial mailing, a trained study interviewer housed within the CCSS Call Center will begin calling non-responders to provide information, answer questions, and encourage participation. Participants will have the opportunity to consent to the study verbally while speaking with the CCSS Call Center. Alternatively, survivors who wish to participate will enroll online via DatStat Connect (the current online data collection tool for the CCSS). Prospective participants will complete an online consent form. After consenting, they will complete a series of short online questionnaires to determine study eligibility. We anticipate needing to recruit 352 participants to reach the targeted enrollment of 320 at 9 weeks and 280 at 6 months. Upon enrollment, participants will be asked to complete all the study activities completely remotely. For the baseline remote evaluation, participants will complete a computerized remote cognitive assessment and will provide a blood sample using the Dried Blood Spot (DBS) method. Participants will be asked to complete online questionnaires and sleep diaries. Participants will be mailed a WHOOP wrist monitor to wear for 7 to 11 consecutive days. Two more identical remote evaluations will occur, one immediately after the intervention is completed and one 6 months after completion of the intervention.

**Study Design:** Randomized Controlled Trial

**Sample Size:** Approximately 352 research participants

**Data Management: Collection of eHealth Data Using the RICE Platform:** Interaction with participants and collection of data will be accomplished using the Research Infrastructure Containing E-interventions (RICE) Platform developed at the Center for Behavioral Health and Technology at the University of Virginia by [name] (Co-Investigator). Through a subcontract with [name] and the University of Virginia, a study-specific module within the RICE Platform will be used for post-enrollment study activities. The platform will be used to: (1) provide access to instructional and demonstration videos; (2) collect data, including questionnaires; (3) implement the SHUTi program (intervention group) and educational program (control group); and (4) secure transmission of data to the study team. The platform allows for input constraints in the tools as well as real-time validation of data formats and ranges, providing real-time feedback to the user if “out-of-range” values are recorded. Participants will need to be able to access the internet on a device of their choosing.

We anticipate enrollment of 352 participants within a 4-year period.

**Human Subjects:** The risk of harm anticipated in the proposed research is not greater than that encountered during daily activities or during the performance of routine physical

**Protocol MNEMONIC and Title: SLEEPWELL: eHEALTH INSOMNIA  
INTERVENTION FOR ADULT SURVIVORS OF CHILDHOOD CANCER: A  
RANDOMIZEDCLINICAL TRIAL**

examinations. Monitoring will be performed by the PI, co-investigators, and the IRB through annual continuing reviews. All study activities will be done completely remotely, and the main requirement is to have internet access, access to a computer or laptop, and access to a smart phone or tablet. During the intervention, participants will be instructed on how to minimize the risk associated with sleep restriction and to contact study staff if they have any significant concerns. As needed, study staff will instruct participants to contact their primary care provider. Participants will not be required to complete any of the assessments they wish to omit, nor will they be required to answer any questionnaire items they do not wish to answer.

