Functionally, the WHOOP devices provide sleep-pattern measures including: SOL, WASO, SE, and total sleep time (TST). Movement triggering the device is relatively high during wakefulness and decreases to near-zero values during sleep. Analysis of actigraphic records reveals sleep-wake patterns that correlate closely with patterns obtained via polysomnographic recordings and behavioral observations. Furthermore, actigraphy is a reliable method for assessing sleep-wake patterns and monitoring of treatment response among insomnia patients. Actigraphy is able to sensitively capture change in sleep-wake patterns before and after behavioral or medical interventions, and actigraphic data from either wrist is highly similar. The mailing of the WHOOP wrist monitors will be coordinated by study personnel at St. Jude in collaboration with the CCSS coordinating center. Participants will receive a WHOOP wrist monitor along with a pre-paid return package. A WHOOP wrist monitor will be mailed at baseline and maintained by the participant until the 6-month follow-up. Participants will download the WHOOP app to their device (smart phone or tablet/iPad with BLE 4.2 or higher) so they can remotely upload their data to a secure cloud-based platform hosted by WHOOP and securely accessible by the study team at St. Jude.

4) Questionnaires to measure fatigue and daytime sleepiness will be completed via the RICE Platform at baseline, post-intervention, and 6-month follow-up. These questionnaires will assess the functional symptoms of insomnia using the Functional Assessment of Chronic Illness Therapy – Fatigue (FACIT-Fatigue) and Epworth Sleepiness Scale (ESS).

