#### SHUTi

SHUTi is a fully automated, interactive and tailored web-based program that incorporates the primary tenets of face-to-face CBT-I, including sleep restriction, stimulus control, cognitive restructuring, sleep hygiene, and relapse prevention. Intervention content is presented in six "Cores," metered out over time. Each Core

was developed to parallel traditional weekly sessions conducted when delivering CBT-I in a face-to-face format, following a similar general structure: 1) examination of Core objectives, 2) review and feedback on homework and sleep diary data from the previous week, 3) teaching of new intervention material, 4) summary of the main points of the Core, and 5) assignment of homework. The participant will have nine weeks to complete the six cores and at week 10 will be asked to complete post-intervention questionnaires/sleep diaries as well as to complete the post intervention remote evaluation. Data will be available on total number of participant logins, sleep diaries completed, and core modules completed. All participants will be able to access human support through UVA for technical difficulties with SHUTi. Intervention content is enhanced through

St. Jude Children's Research Hospital

IRB NUMBER: 19-0121

IRB APPROVAL DATE: 05/04/2021

a variety of interactive features, including personalized goal-setting, graphical feedback based on reported symptoms, animations and illustrations to enrich comprehension, quizzes to test and enhance user knowledge, vignettes to promote identification with material, and video-based expert explanations. Weekly automated emails are also sent to increase engagement and encourage program adherence. However, no human support will be provided to increase treatment adherence. Removing human support from provision of care can vastly increase the ability to widely disseminate treatment, however, it may be associated with reduced adherence. Despite this, a recent study of SHUTi with breast cancer survivors indicated that intervention group participants completed 4.1 (SD = 2.5) cores, with 82.1%, 75.1%, 67.2%, 64.2%, 62.7%, and 59.7% completing cores 1, 2, 3, 4, 5, and 6, respectively. The number of cores completed was associated with improvements in insomnia symptoms. Therefore, we will complete a sensitivity analysis to examine the impact of treatment adherence on insomnia symptoms.

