## 7.0 SAFETY AND ADVERSE EVENT REPORTING REQUIREMENTS

### 7.1. Reporting Adverse Experiences and Deaths to St. Jude IRB

7.1.1. Only “unanticipated problems involving risks to participants or others” referred to hereafter as “unanticipated problems” are required to be reported to the St. Jude IRB promptly, but in no event later than 10 working days after the investigator first learns of the unanticipated problem. Regardless of whether the event is internal or external (for example, an IND safety report by the sponsor pursuant to 21 CFR 312.32), only adverse events that constitute unanticipated problems are reportable to the St. Jude IRB. As further described in the definition of unanticipated problem, this includes any event that in the PI’s opinion was:

- Unexpected (in terms of nature, severity, or frequency) given (1) the research procedures that are described in the protocol-related documents, such as the IRB-approved research protocol and informed consent document, as well as other relevant information

available about the research; (2) the observed rate of occurrence (compared to a credible baseline for comparison); and (3) the characteristics of the subject population being studied; and

- Related or possibly related to participation in the research; and
- Serious; or if not serious suggests that the research places subjects or others at a greater risk of harm (including physical, psychological, economic, or social harm) than was previously known or recognized.

Unrelated, expected deaths do not require reporting to the IRB. Though death is “serious”, the event must meet the other two requirements of “related or possibly related” and “unexpected/unanticipated” to be considered reportable.

Deaths meeting reporting requirements are to be reported immediately to the St. Jude IRB, but in no event later than 48 hours after the investigator first learns of the death.

7.1.2. The following definitions apply with respect to reporting adverse experiences:

7.1.2.1. **Serious Adverse Event:** Any adverse event temporally associated with the subject’s participation in research that meets any of the following criteria:

- results in death;
- is life-threatening (places the subject at immediate risk of death from the event as it occurred);
- requires inpatient hospitalization or prolongation of existing hospitalization;
- results in a persistent or significant disability/incapacity;
- results in a congenital anomaly/birth defect; or

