- any other adverse event that, based upon appropriate medical judgment, may jeopardize the subject’s health and may require medical or surgical intervention to prevent one of the other outcomes listed in this definition (examples of such events include: any substantial disruption of the ability to conduct normal life functions, allergic bronchospasm requiring intensive treatment in the emergency room or at home, blood dyscrasias or convulsions that do not result in inpatient hospitalization, or the development of drug dependency or drug abuse), a congenital anomaly/birth defect, secondary or concurrent cancer, medication overdose, or is any medical

event which requires treatment to prevent any of the medical outcomes previously listed.

7.1.2.2. **Unexpected Adverse Event:**

- Any adverse event for which the specificity or severity is not consistent with the protocol-related documents, including the applicable investigator brochure, IRB approved consent form, Investigational New Drug (IND) or Investigational Device Exemption (IDE) application, or other relevant sources of information, such as product labeling and package inserts; or if it does appear in such documents, an event in which the specificity, severity or duration is not consistent with the risk information included therein; or
- The observed rate of occurrence is a clinically significant increase in the expected rate (based on a credible baseline rate for comparison); or
- The occurrence is not consistent with the expected natural progression of any underlying disease, disorder, or condition of the subject(s) experiencing the adverse event and the subject's predisposing risk factor profile for the adverse event.

7.1.2.3. **Internal Events:** Events experienced by a research participant enrolled at a site under the jurisdiction of St. Jude IRB for either multicenter or single-center research projects.

7.1.2.4. **External Events:** Events experienced by participants enrolled at a site external to the jurisdiction of the St. Jude Institutional Review Board (IRB) or in a study for which St. Jude is not the coordinating center or the IRB of record.

7.1.2.5. **Unanticipated Problem Involving Risks to Subjects or Others:** An unanticipated problem involving risks to subjects or others is an event which was not expected to occur and which increases the degree of risk posed to research participants. Such events, in general, meet all of the following criteria:

- unexpected;

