### **8.2. Study Monitoring**

#### **Lowest Risk:**

This study is considered lowest risk for monitoring purposes. The Principal Investigator (PI) and study team are responsible for ensuring protocol and regulatory compliance. The St. Jude monitoring group will not monitor this study. The study team is responsible for data quality and will meet as needed to review case histories or quality summaries on participants and will generate minutes which are signed by the PI.

Protocol continuing reviews by the Institutional Review Board (IRB) and Scientific Review Committee (CT-SRC) will occur at least annually. In addition, Unanticipated Problems and/or Serious Adverse Event reports are reviewed by the IRB.

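### No adverse-event question is scheduled at any time, and no sleepiness scale between baseline and week 10, so the trial cannot form a solicited adverse-event rate by arm

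*Combined protocol and SAP*

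**What the plan says.** The Human Subjects paragraph of the protocol summary states that "participants will be instructed on how to minimize the risk associated with sleep restriction" and asks participants "to contact study staff if they have any significant concerns". Section 4.4 (SHUTi) lists sleep restriction among the programme's components and adds: "The participant will have nine weeks to complete the six cores". The post-intervention questionnaires follow at week 10.

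Section 4.3 fixes the timing of the sleepiness and fatigue scales: "Questionnaires to measure fatigue and daytime sleepiness will be completed via the RICE Platform at baseline, post-intervention, and 6-month follow-up". The table in Section 5.2 and Appendix I agree with this. Neither has a row for adverse events.

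Section 7.1 governs reporting to the IRB and is limited to unanticipated problems. In judging whether an event is unexpected, Section 7.1.1 refers to "the observed rate of occurrence (compared to a credible baseline for comparison)". Section 7.1.2.2 gives as one alternative: "The observed rate of occurrence is a clinically significant increase in the expected rate". No baseline or expected rate is stated.

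On oversight, the summary says "Monitoring will be performed by the PI, co-investigators, and the IRB through annual continuing reviews", and Section 8.2 says "The St. Jude monitoring group will not monitor this study". Section 9 contains no safety analysis.

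**The concern.** The plan recognises a risk from part of its intervention but schedules nothing that asks whether the risk occurred. All activities are remote, SHUTi runs without a therapist, and the human support offered in Section 4.4 is for technical problems. Information about harm during the programme therefore depends on a participant judging a concern significant and getting in touch.

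Two things are at stake. First, a report of few or no harms could reflect not having asked. This matters because the summary expects the programme to be scaled to the wider survivor population, and Section 2.2 says no study has yet examined CBTi for insomnia in long-term survivors of childhood cancer. Second, other provisions need this information. Section 6.1.5 lets the PI remove a participant who is worsening or for whom continuing would be harmful, and Section 7.1 refers to an observed rate of events. No scheduled collection supplies either systematically during the intervention.

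**Working it through.** This is mainly a check of the schedule. The plan states no safety rate or safety sample size to reproduce. Its power figures concern the ISI and are not in dispute: with 80 per arm, (1.960 + 0.842) × √(2/80) = 0.443, against the stated 0.45.

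**Step 1: scheduled collection (Sections 4.3, 4.4, 5.2; Appendix I).** There are three assessment points: baseline, week 10 and 6 months.
- Adverse-event questions at any point: 0.
- Epworth or FACIT-Fatigue administrations after baseline and before week 10: 0.
- Participants with no Epworth after baseline under the assumed 10% dropout: 352 × 0.10 ≈ 35. The plan's rounded 320 evaluable gives 352 − 320 = 32.

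**Step 2: what else exists during the programme.**
- *Sleep diary (Section 4.3).* It runs in both arms and includes naps and a rating of feeling refreshed. Ten entries are required before the intervention. After that, daily completion is only encouraged. It has no sleepiness scale and no event item, and no safety review is assigned.
- *Staff tracking through RICE (Section 4.4).* It covers both arms but is not described as a safety check.
- *Participant contact (Human Subjects paragraph).* It is available but unsolicited.
- *Study-team meetings (Section 8.2).* They are held as needed, with no stated safety data feed.

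**Step 3: the rate element of Section 7.1.** An observed rate needs a count from people who were asked, divided by the number asked. Step 1 shows that nobody is asked on a schedule. The comparator is also missing, since no baseline or expected rate is given.

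**Step 4: size, on assumed figures.** The documents give no event rate, so this is illustration only. Arm size is 352 / 2 = 176, taking 1:1 allocation as implied by equal arms in the power section.

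If nobody reports an event among n people who were all asked, the one-sided 95% upper bound on the rate is 1 − 0.05^(1/n).
- n = 176: 1.7%.
- n = 176 × 0.9 ≈ 158, allowing for 10% dropout: 1.9%.

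If only a fraction c of events is volunteered, the bound applies to c times the true rate, so the true rate is bounded by 1.69% / c. That is 3.4% at c = 0.5 and 6.8% at c = 0.25. The plan gives no basis for choosing c.

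Incomplete capture also weakens any comparison of arms, even when it is equal in both. Power at two-sided 0.05 with 176 per arm is Φ{[d − 1.96√(2p̄(1−p̄)/n)] / √[(p₁(1−p₁)+p₂(1−p₂))/n]}, where p₁ and p₂ are the captured rates, p̄ is their mean and d is their difference:

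| True rates (assumed) | All captured | Half | Quarter |
|---|---|---|---|
| 5% vs 15% | 0.88 | 0.58 | 0.32 |
| 10% vs 20% | 0.75 | 0.43 | 0.23 |
| 5% vs 12% | 0.66 | 0.37 | 0.21 |

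**The case against.** The strongest reply is that this is a minimal-risk behavioural trial. The summary rates the risk as no greater than that of daily life, Section 8.2 places the study in the lowest monitoring category, and there is no safety objective. The named risk comes with instruction and a contact route, so the text does not contradict itself. Section 7.1 reads as institutional boilerplate: its examples include tumour staging and a contaminated study drug. It is weak evidence that this trial meant to calculate rates. All of that stands. It argues for a light remedy, but does not supply an event count by arm.

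A reader might also infer more than the documents support:
- *That the whole nine weeks is a period of sleep restriction.* Nine weeks is the time allowed for all six cores. The documents do not say when restriction starts or ends, or that sleepiness rises and then resolves before week 10.
- *That sleepiness cannot be compared between arms.* Section 9.1 plans comparisons of diary, actigraphy, fatigue and daytime sleepiness at post-intervention and 6 months. The gap concerns adverse events at all times and scaled sleepiness during the programme.
- *That spontaneous reports will be skewed because only SHUTi users are warned.* The Human Subjects paragraph does not limit the instruction or the contact route to one arm. Reporting may differ by arm, but neither direction nor size can be derived.
- *That the Section 7.1 definitions are unworkable.* Frequency is one consideration alongside nature and severity in Section 7.1.1, and rate is one of three alternatives in Section 7.1.2.2. The PI can still judge individual events.
- *That sleep restriction is the only risk recognised.* Consent pages are not in the supplied text, so this cannot be checked.

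**Conclusion.** The point holds in a limited form. No adverse-event question is scheduled at any time, and no sleepiness or fatigue scale falls between baseline and week 10. In-programme harm is learned only through participant contact, apart from an optional diary and staff tracking that carry no stated safety role. The trial cannot form a solicited adverse-event rate by arm, and the rate element of Section 7.1 lacks a systematic numerator and a stated comparator.

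The schedule counts come directly from the documents. The numerical illustrations rest on assumed event rates, assumed capture fractions and 1:1 allocation. They show the kind of information lost and do not predict what this trial would find. This is a worthwhile, inexpensive improvement to the safety information. It does not touch the validity of the primary ISI analysis or the sample size.

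**What to change.** Add one short fixed question on accidents, near-accidents, injuries, falls or new medical care to the RICE questionnaires. Ask it once at a fixed mid-programme time and again at week 10 and 6 months, on the same calendar days from programme start in both arms and not tied to core completion. Section 4.2.1 indicates that RICE already has the questionnaire, timing and e-mail tools.

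Add an adverse-event row to the Section 5.2 table and to Appendix I. State in Section 8 that the existing study team reviews the responses. State in Section 9 that counts will be tabulated by arm together with the number who answered, since participants may skip items. The table should be descriptive. If the rate element of Section 7.1 is to be used, say which counts feed it and what comparator applies.

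A mid-programme Epworth is optional. One fixed administration may miss the relevant period in people who work through the cores at different speeds, so its value is more debatable than that of the event question. Any clinical action on a response is for the sponsor to decide.

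The cost is a protocol and RICE schedule amendment, a few minutes of participant time, some review time for the existing team, and slight reactivity to an extra questionnaire, which should be equal in both arms. No visit or device is added.
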